3.6 Screen failure procedures

If a patient does not meet inclusion criteria at enrollment, normal clinical care will resume with no detriment to the patient.

4 STUDY EVALUATIONS AND MEASUREMENTS (how measurements will be made)

- List variables that will be abstracted from medical charts

Page **12** of **20**

Baseline demographics including age, sex, race, BMI, smoking history, among others will be recorded from the medical chart and verified with the patient on the day of enrollment.

- Describe baseline evaluation

Baseline evaluation will include identifying surgical site, evaluating if surgical site is optimal for study inclusion, assessment of patient's overall general health,

- Describe how measurements will be taken.

Patient's upload a photo of their wound with each online survey they complete, as well answers to questions such as pain with wound dressing changes on a scale 1-10. Wound measurements and wound characterization for the primary and secondary endpoints will then be completed at the conclusion of the study by the PI. Other questions and data will be inputted by patients directly on the survey for future statistical evaluation.

- Describe rating scales, tests, psychological tools, laboratory evaluations, etc.

The previously-described PUSH, Wound QOL, and NRS primary endpoints will all be recorded and extrapolated from the online surveys submitted by patients at scheduled intervals.

STATISTICAL CONSIDERATIONS

Our study is powered to detect an effect on our primary endpoints, pain and quality of life. Although we will use the Wound Quality of Life (QoL) survey for our main analysis, as it is more comprehensive and we think readers will find it more persuasive, we don't have direct data on what to expect. Rather, we do have a strong sense, from clinical experience, of what will happen with pain. Using the 0-10 numerical pain scale, we believe the non-stick dressing will reduce pain ratings by 1.3 points at the two-week checkup and estimate the historical SD at that visit is 1.4 units, implying a .93 SD reduction. We calculate we will need 28 patients per arm to achieve 80% power. We add 2 more to account for two planned covariates (pelvic area vs armpit, and initial wound size). Since we expect approximately 20% dropout, we will plan to recruit approximately 74 patients.

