6 STUDY INTERVENTION ADMINISTRATION

- Randomization procedures

A stratified block randomization will take place after the principal investigator has left the surgical room following surgery. Randomization will be performed by the research fellow. Each participant is assigned to a particular stratum based on wound size and location, two important covariates to control for in statistical analysis given these variables can impact the Wound QOL survey and other results significantly. After strata assignment, randomization is completed via a RedCap algorithm. A detailed outline of the randomization process and groups can be found in **Figure 1**.

- Blinding procedures

Following the surgical procedure, the principal investigator will exit the exam room. The principal investigator will thus be blinded to the wound dressing technique as he will not be present for bandaging administration, but the patient will not be blinded as they themselves will be administering the bandaging at home.

- Unblinding procedures

If at any point unblinding occurs, the involved patient will be notified that their further participation in the study is voluntary but their patient data can no longer be used for analysis. There is no penalty or direct harm anticipated to the patient because of unblinding. They can continue to bandage their wound as assigned during randomization or alternatively if desired.

- Premature Study Closure

If any of the groups are showing significantly worse outcomes with regard to changes in pain or days to surgical wound resolution before the end of the recruitment period, the study will be ended prematurely.

- Subject Withdrawal

If a subject fails to complete a their one-week postoperative survey or are unable to complete the assigned wound care for a full week, they will be withdrawn from the study. All subjects will have the option to withdraw from the study at any time that they wish.

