8. DATA COLLECTION AND MANAGEMENT

All patient data collected in this study will be stored within the secure research software RedCap. Data access will be restricted to the research fellow as the primary data input source. Downloaded data will be secured on the UNC hospital cloud and only de-identified data will be sent via email. The principal investigator will not have access to any patient data until the de-identified data is provided for analysis at the conclusion of the study. Data will be coded according to established coding protocol.

Quality assurance is built into data collection process by ensuring that source data documents capture data in established/standardized format that aligns with establish coding standards.

Project manager will monitor data throughout the study to ensure all data is source verified. Data will be monitored after the first patient is enrolled, after the first 50% of patients are enrolled, and again at the end of the study (last patient, last follow-up). Regular meetings will be scheduled to ensure that data is cleaned along the way (not just at the end).

Data archiving: coded data will be stored on the Department share drive which is backed up and maintained by the school of medicine. Only study personnel will have access to the study data.

Data from patient surveys will all be collected at the same time so it is unlikely that we will be missing many data points. If patients fail to enter data at specific time points on their surveys we will use the previous value carried forward to the missing data point. The data for patients who do not return their surveys will not be included in the study analysis as it will be too difficult to correctly estimate their responses.

Data Safety Monitoring Plan

We will be compiling and monitoring data on responses on an ongoing basis and reviewing every 2-3 weeks. If one group is demonstrating significantly worse outcomes before the planned end of the enrollment period, we will end the study early and report the results available at that time.

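### The missing-data rules do not say whether one unreturned survey removes the visit or the whole patient, and no sensitivity analysis covers dropout that differs by arm

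*Combined protocol and SAP*

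**What the plan says.** Section 8 (Data Collection and Management) holds two rules. The first starts "If patients fail to enter data at specific time points on their surveys" and continues "we will use the previous value carried forward to the missing data point". The second reads "The data for patients who do not return their surveys will not be included in the study analysis", on the ground that "it will be too difficult to correctly estimate their responses". Just before them, the section says that few data points should be missing because survey answers are collected together.

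Section 6 (Subject Withdrawal) withdraws anyone who "fails to complete a their one-week postoperative survey or are unable to complete the assigned wound care for a full week". Section 3.5 allows withdrawal at any time. Neither says whether surveys returned before withdrawal are analysed. Section 6 (Unblinding procedures) separately bars a patient's data from analysis once unblinding occurs.

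Statistical Considerations sets recruitment at about 74 with the words "Since we expect approximately 20% dropout". Section 6 calls wound size and location "two important covariates to control for in statistical analysis". No model for incomplete repeated measures, no imputation model and no sensitivity analysis is described.

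**The concern.** The natural reading is that carry-forward covers entries skipped on a returned survey and exclusion covers surveys not returned. The reference to specific time points leaves some doubt, because each survey is itself a time point. Even on the natural reading, a patient who returns weeks 1 and 2 and then stops could lose weeks 4 and 6 only, or leave the analysis altogether.

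This matters if dropout differs by arm. Patients are not blinded. Section 1.3 expects dressing pain especially with wet-to-dry and lets patients opt out of the bandaging protocol. Each rule then has its own weakness:

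- **Carry-forward.** If scores fall as wounds heal, it places an early, worse score at a late visit and treats it as observed. The arm with more dropout looks worse. If that arm is wet-to-dry, non-inferiority of petrolatum on PUSH becomes easier to claim.
- **Exclusion.** It biases the comparison only if dropout also depends on outcome. The direction is opposite to carry-forward if worse-off patients leave, and the same if better-off patients leave.

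The Data Safety Monitoring Plan has the team "monitoring data on responses on an ongoing basis and reviewing every 2-3 weeks" and comparing groups. For the survey endpoints, an open rule could therefore be settled after arm results are known.

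**Working it through.** **Inputs from the documents.** 74 enrolled (Section 2.3). 20% dropout; 28 per arm plus 2 for covariates; 97.5% CI half-width of 0.61 SD; 0.84 SD excluded with 80% power; pain effect of 1.3 points with SD 1.4 at week 2 (Statistical Considerations).

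**Assumed, because the documents do not give them.** PUSH means 12/10/7/4 at weeks 1/2/4/6, SD 3, correlation 0.6, 37 per arm, arms with the same course. Dropout in wet-to-dry/petrolatum is 25%/15% or 30%/10%, split evenly after weeks 1 and 2 unless stated. Bias is wet-to-dry minus petrolatum, so a positive value favours petrolatum.

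**1. The plan's own figures.** 2 × (28 + 2) = 60, and 60/0.8 = 75. If the extra 2 is a total, 58/0.8 = 72.5, so 73. The stated 74 lies between. At 28 per arm the half-width is 2.306 × √(2/28) = 0.616 SD, close to the stated 0.61. At 37 per arm it would be 0.532 SD. The stated precision therefore fits completers, which supports the exclusion reading. The sample size is not in question.

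**2. Visit or patient.** With 20% dropout, the week-2 set is 74 under carry-forward, 74 × 0.9 ≈ 67 if the visit is removed, and 74 × 0.8 ≈ 59 if the patient is removed. If 5% or 10% independently miss each of weeks 2, 4 and 6, removing the visit loses 5% or 10% at that visit. Removing the patient loses 1 − 0.95³ = 14% or 1 − 0.90³ = 27%.

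**3. Exclusion, week 6 (simulated, 25/15 and 30/10).**

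| Dropout depends on | Bias, points |
|---|---|
| nothing (random) | 0 and 0 |
| week-1 score, worse leave | −0.19 and −0.38 |
| week-1 score, better leave | +0.20 and +0.38 |
| week-6 score, either direction | about 0.31 and 0.64 in size |

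**4. Carry-forward applied to dropouts, week 6.** Bias = (difference in dropout) × ((12 + 10)/2 − 4) = (difference) × 7.

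- All leave after week 1 or 2: 0.10 × 7 = 0.70 and 0.20 × 7 = 1.40 points.
- Half leave before week 1, so nothing can be carried forward and they leave the analysis: (0.125/0.875 − 0.075/0.925) × 7 = 0.43 and (0.15/0.85 − 0.05/0.95) × 7 = 0.87 points.
- All leave before week 1: 0.

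**5. Effect on the non-inferiority decision, first case of step 4.** Take 0.84 SD as an assumed margin and let petrolatum truly be worse by that amount at every visit. Carry-forward mixes early and late scores, so the week-6 variances rise from 9 to 18.44 and 15.40 (25/15) or 19.59 and 13.51 (30/10). The standard errors are √(33.84/37) = 0.956 and √(33.10/37) = 0.946. The chance of false non-inferiority is Φ(0.70/0.956 − 2.241) ≈ 6.6% and Φ(1.40/0.946 − 2.241) ≈ 22%. Simulation with the t-test gives about 6% and 22%. The nominal rate is 1.25%.

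**6. Week 2, the only visit with a stated effect.** The largest bias under exclusion arises when the whole patient is removed: 0.384 PUSH points, or 0.384/3 = 0.13 SD. On the pain scale that is 0.13 × 1.4 ≈ 0.18 points against the expected 1.3.

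**7. Equal dropout, 20/20.** Every method stays within 0.036 points of zero, which is simulation noise.

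**8. Repeated-measures likelihood, week 6.** Bias is at most 0.013 points when dropout is random or depends on an observed score. It is about 0.20 and 0.41 when dropout depends on the unobserved week-6 score, against 0.31 and 0.64 under exclusion.

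**The case against.** The strongest reply is that the text already has a sensible split, skipped entries versus unreturned surveys, and that the larger figures above belong to the less natural reading. That stands: the exclusion figures are the ones to weigh first.

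Arm-related dropout may also be milder than feared. Section 1.3 offers further pain treatment and other wound management, and its opt-out is from the bandaging protocol, not from the surveys. Section 2.4 excludes patients with a dressing preference or past intolerance. This also stands, so neither the size nor the direction of any difference can be predicted.

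A reader might infer three stronger things that the documents do not support:

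- **False-positive rates of 11% and 30%.** These arise from carry-forward with a two-sided 5% difference test on PUSH. The plan's PUSH question is non-inferiority with a 97.5% CI, and Section 6 withdraws patients who miss week 1, for whom there is nothing to carry forward.
- **A conflict between Sections 2.1 and 3.3 on the survey schedule.** They agree: Section 3.3 also allows later surveys if needed.
- **A known bias towards petrolatum.** No dropout by arm and no score trajectories are given.

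What the reply leaves untouched is the visit-or-patient question, the use of data collected before withdrawal, and the absence of any sensitivity analysis.

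**Conclusion.** The point holds as a gap that should be closed; it does not show that the comparison is biased. The plan leaves open how a patient who stops part-way is analysed, while expecting about 20% dropout and giving a plausible reason for it to differ by arm.

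On the more natural reading, the illustrative week-6 bias runs from 0 to about 0.64 PUSH points (0.21 of the assumed SD of 3). It would be larger only if carry-forward were applied to dropouts, and then it depends heavily on how many leave before week 1. At week 2 the effect on pain is small next to the expected difference. All sizes rest on the assumed means, SD, correlation and dropout split, none of which the documents supply.

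**What to change.** Replace both Section 8 rules with wording such as:

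> Each primary endpoint is analysed with a mixed model for repeated measures (or multiple imputation with the same variables), using every observed survey from randomised patients with at least one survey, including surveys returned before withdrawal. Terms are arm, visit, arm-by-visit, wound location and initial wound size. The arm contrast is read at one pre-named visit per endpoint. PUSH after documented closure is scored as closed.

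The closure sentence is needed because Section 2.1 sends questionnaires until the wound has closed, so a missing later survey may mean healing.

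In addition:

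- Reconcile this wording with the Section 6 rule that removes unblinded patients' data, and report how many patients per arm that rule removes.
- Report missingness by arm, visit and reason, including patients with no survey, whom the model cannot use.
- Add one sensitivity analysis that shifts imputed petrolatum PUSH values towards worse. The model reduces but does not remove bias when dropout depends on unobserved scores.
- Keep carry-forward only as a sensitivity analysis.

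**Cost.** SAP wording and slightly more analysis work; no new data. A simpler covariance structure may be needed at this sample size. The PUSH conclusion may prove less robust. With 74 already enrolled, the change must be labelled post hoc for any endpoint whose results by arm have been seen. This is most likely for pain and Wound-QoL, which are under periodic review; PUSH is scored at the end of the study, so its rule may still be set beforehand.

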9. RECRUITMENT STRATEGY

No active recruitment outside of normal clinical practice will occur. Subjects with a diagnosis of hidradenitis suppurativa will be identified in a subspecialty clinic dedicated to hidradenitis suppurativa in the UNC Dermatology Clinic. Patients will be invited to participate in this study on the day of surgery. However, patients will be offered 6-weeks supply of bandaging supplies as partial compensation for their participation. No incentives or reimbursements are directly provided that would be prorated. Patients will not be required to return unused bandaging supplies. Bandaging materials will be required for all patients. The cost of materials or potential for them to be sold is not high enough to significantly coerce patients. Providing the appropriate materials will increase the odds that patients will follow the regimens and not find an alternative that might be easier to obtain or slightly less expensive. Since we will be enrolling older children ages 16-17, we will plan on providing compensation to the subjects and/or the person helping them care for their wounds since they will be providing assent and are likely to complete their questionnaires themselves. Patients will not incur any additional costs because of study participation.

Written informed consent will be obtained prior to unroofing procedures in an outpatient clinic setting. Consent will be obtained by a research fellow. Consent forms will be printed off and signed with pen in person by the patient and the research fellow. A patient's ability to provide consent will be assessed prior to and during the consent process. If a patient cannot acknowledge understanding of the risks and benefits of participation to the consenter, they will be consented or included in the study.

Children suffer from hidradenitis suppurativa, and the onset of the disease is often in the teenage years. Children \geq 16 years of age will be included in study recruitment. Specific assent and consent forms have been composed and approved by the UNC IRB that must be printed and signed by both the patient and a parent/legal representative prior to the child participating in the research study. As determined by the UNC IRB, there are no additional or added risks associated with a child's participation in the research study as compared to an adult. Consent from children will require that both the child and a parent/guardian are present in the room during the consent process. Consent forms and assent forms will both be signed.

By signing the informed consent document, the patient will agree that some of the information generated by participating in this study and/or a copy of the consent form may be included in their medical record and that this information may be viewed by other physicians or caregivers who provide healthcare services to them. This will allow the doctors caring for them to know what study medications or tests they may be receiving as a part of the study and know how to take care of them if they have other health problems or needs during the study.

Participants will be asked to sign a separate form ("HIPAA Authorization") to allow researchers to review their medical records.

11. PLANS FOR PUBLICATION

Manuscript submission for publication is planned within 24 months following closure of the study.

APPENDIX

Arms	Assigned Interventions
Active Comparator: Wet- to-dry Dressings	Device: Wet-to-Dry Dressings
Participants in this arm will receive standard of care wet-to-dry dressings.	This dressing technique involves moistening a piece of gauze with normal saline or other cleansing solution, placing the moistened gauze on the wound, allowing the gauze to dry, and then removing and replacing the bandage regularly over a period of days to weeks
Experimental: Petrolatum with Non-Stick Gauze	Device: Petrolatum with Non-Stick Gauze
Participants in this arm will receive petrolatum with non-stick gauze.	This dressing approach involves applying a thick layer of petrolatum to the wound once or twice daily to maintain a moist wound base. After placement of petrolatum, the wound is covered with nonadherent gauze and tape or another bordered dressing.

Figure 1. Randomization Process
